### 5.1.1 Uproleselan (GMI-1271): IV over 20 minutes (±2 minutes)

Days: 1-8

On Day 1, uproleselan (GMI-1271) will be administered as a single dose 24 hours ± 2 hours prior to the first dose of chemotherapy. Since patients will receive a single dose of IT cytarabine or ITT on Day 0 of Cycle 1, it is recommended, but not required, that systemic therapy begin at least 24 hours after the intrathecal therapy.

On Days 2-6, uproleselan (GMI-1271) will be administered every 12 hours ±1 hour starting 2 hours ± 15 minutes *prior* to initiation of chemotherapy (fludarabine and cytarabine).

On Days 7-8, uproleselan (GMI-1271) will be administered every 12 hours ±1 hour as single agent.

At least 22 hours ± 2 hours should pass between uproleselan (GMI-1271) dose on Day 1 and the first uproleselan (GMI-1271) dose on day 2. A total of 15 uproleselan (GMI-1271) doses will be administered on Days 1-8.

If ≤6 hours have elapsed since the time of the planned dose, the dose should be given. If uproleselan (GMI-1271) and chemotherapy are held for more than 72 hours for medical reasons, the study chair or vice chair should be consulted before restarting uproleselan (GMI-1271). If chemotherapy is held for less than 72 hours and is restarted, uproleselan (GMI-1271) may be restarted when chemotherapy is restarted, and the original schedule continued if possible. For questions on restarting uproleselan (GMI-1271), the chair or vice chair should be consulted.

### 5.1.2 Fludarabine: IV over 30 minutes once daily

Days: 2-6

Dose: age-based dosing

Age at enrollment	Dose
< 1 year	1 mg/kg/dose
≥ 1 year	30 mg/m  /dose

### 5.1.3 High Dose Cytarabine: IV infusion over 1-3 hours once daily

Days: 2-6

Dose: age-based dosing

Age at enrollment	Dose
< 1 year	67 mg/kg/dose
≥ 1 year	2000 mg/m  /dose

***Please note:*** Begin cytarabine infusion 4 hours after the start of the fludarabine infusion. Following/during high-dose cytarabine, chemical conjunctivitis may occur. **Administer steroid eye drops (0.1% dexamethasone or 1% prednisolone ophthalmic solution), 2 drops to each eye every 6 hours, beginning immediately before the first dose and continuing for 24 hours after the last dose of cytarabine.** If patient does not tolerate steroid eye drops, artificial tears may be administered on an every 2-4 hour schedule. See the Chemotherapy Administration Guidelines (CAG) on the COG website at:

Page 25

THIS PROTOCOL IS FOR RESEARCH PURPOSES ONLY, SEE PAGE 1 FOR USAGE POLICY

<https://cogmembers.org/files/disc/Pharmacy/ChemoAdminGuidelines.pdf> for special precautions and suggestions for patient monitoring during the infusion. As applicable, also see the CAG for suggestions on hydration, or hydrate according to institutional guidelines.

#### **5.1.4 Intrathecal Therapy: IT**

CNS 1 patients: Day 0 and 28

CNS 2/3 patients: Days 0, 7, 14, 21, 28

All patients will receive intrathecal therapy with either IT cytarabine ([Section 5.1.4.1](#)) or triple intrathecals with methotrexate/hydrocortisone/cytarabine (ITT) ([Section 5.1.4.2](#)) in this study according to the schedule above. The choice between IT cytarabine vs triple IT therapy is up to the treating physician's discretion.

Patients will receive a single dose of IT cytarabine or ITT on Day 0 of Cycle 1. It is recommended, but not required, that systemic therapy with uproleselan (GMI-1271) begin at least 24 hours after the intrathecal therapy.

If the patient received IT cytarabine or triple IT therapy during their diagnostic workup within 14 days of starting protocol therapy, then they do not need additional Day 0 IT therapy.

#### **CNS2/3:**

Patients with CNS2/3 will receive IT cytarabine or ITT once weekly starting on Day 0 until the CSF is clear of blasts (CNS1 status) on 2 consecutive LPs. The choice between IT cytarabine vs triple IT therapy is up to the treating physician's discretion. A minimum of 4 weekly intrathecal treatments must be given with a maximum of 6 weekly intrathecal treatments per cycle; these weekly treatments may carry over into Cycle 2 as needed to achieve CNS1 status. If the patient received IT cytarabine or ITT during diagnostic workup within 14 days of starting protocol therapy, then that intrathecal treatment can count as the Day 0 dose and counts within the minimum of 4 and maximum of 6 intrathecal treatments.

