
## EXPERIMENTAL DESIGN SCHEMA

**Table 1 – Experimental Design Schema**

Each Cycle (28 days)						
	Uproleselan (GMI-1271) IV	Fludarabine IV	Cytarabine IV	Cytarabine IT	IT Triples	Leucovorin PO or IV
Day 0				once daily 	once daily 	
Day 1	once daily					24 and 30hrs post ITT 
Day 2	q12hr	once daily	once daily			
Day 3	q12hr	once daily	once daily			
Day 4	q12hr	once daily	once daily			
Day 5	q12hr	once daily	once daily			
Day 6	q12hr	once daily	once daily			
Day 7	q12hr			Weekly 	Weekly 	
Day 8	q12hr					24 and 30hrs post ITT 
Day 9						
...						
Day 14				Weekly 	Weekly 	
Day 15						24 and 30hrs post ITT 
Day 21				Weekly 	Weekly 	
Day 22						24 and 30hrs post ITT 
Day 28				Weekly 	Weekly 	
Day 29 						24 and 30hrs post ITT 

 Choice between IT Cytarabine OR IT Triples is up to the treating physician's discretion. Weekly intrathecal chemotherapy treatments are for CNS 2/3 patients ONLY. A minimum of 4 and a maximum of 6 intrathecal treatments may be given (count includes day 0 IT and may carry over into Cycle 2 of chemotherapy).

 Down syndrome patients ONLY. Administer 24 & 30 hours after each IT Triples.

 End of cycle bone marrow for disease assessment may be performed any day between Day 28-35.

 Day 28 lumbar puncture can be done at the same time as the end of cycle bone marrow assessment between day 28-35.

A cycle of therapy is considered to be 28 days. Upon count recovery, patients may receive a second cycle of uproleselan (GMI-1271) in combination with fludarabine and cytarabine if there is evidence of clinical benefit in the opinion of the treating physician and eligibility criteria are met for organ function criteria.

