## 5.0 TREATMENT PLAN

### 5.1 Overview of Treatment Plan

**Table 2 – Experimental Design Schema**

Each Cycle (28 days)						
	Uproleselan (GMI-1271) IV	Fludarabine IV	Cytarabine IV	Cytarabine IT	IT Triples	Leucovorin PO or IV
Day 0				once daily 	once daily 	
Day 1	once daily					24 and 30hrs post ITT 
Day 2	q12hr	once daily	once daily			
Day 3	q12hr	once daily	once daily			
Day 4	q12hr	once daily	once daily			
Day 5	q12hr	once daily	once daily			
Day 6	q12hr	once daily	once daily			
Day 7	q12hr			Weekly 	Weekly 	
Day 8	q12hr					24 and 30hrs post ITT 
Day 9						
...						
Day 14				Weekly 	Weekly 	
Day 15						24 and 30hrs post ITT 
Day 21				Weekly 	Weekly 	
Day 22						24 and 30hrs post ITT 
Day 28				Weekly 	Weekly 	
Day 29 						24 and 30hrs post ITT 

 Choice between IT Cytarabine OR IT Triples is up to the treating physician's discretion. Weekly intrathecal chemotherapy treatments are for CNS 2/3 patients ONLY. A minimum of 4 and a maximum of 6 intrathecal treatments may be given (count includes day 0 IT and may carry over into Cycle 2 of chemotherapy).

 Down syndrome patients ONLY. Administer 24 & 30 hours after each IT Triples.

 End of cycle bone marrow for disease assessment may be performed any day between Day 28-35.

 Day 28 lumbar puncture can be done at the same time as the end of cycle bone marrow assessment between day 28-35.

A cycle of therapy is considered to be 28 days. A cycle may be repeated for a total of 2 cycles, up to a total duration of therapy of approximately 2 months.

Drug doses of uproleselan (GMI-1271) should be adjusted based on the weight measured within 7 days prior to the beginning of each cycle. Drug doses of fludarabine and cytarabine should be adjusted based on the BSA (calculated from the height and weight) or weight (patients < 1 year) measured within 7 days prior to the beginning of each cycle. Drug doses of intrathecal cytarabine, methotrexate and hydrocortisone should be based on the age of the patient at the time of administration.

THIS PROTOCOL IS FOR RESEARCH PURPOSES ONLY, SEE PAGE 1 FOR USAGE POLICY

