### 5.5.2.2 **Note:** Grade 3 or 4 febrile neutropenia will not be considered a dose-limiting toxicity.

## 5.6: THERAPY DELIVERY MAPS (TDMS) FOR CYCLE 1-2

**Therapy Delivery Map – Cycle 1-2** A cycle of therapy is considered to be 28 days. A cycle may be repeated for a total of 2 cycles, up to a total duration of therapy of approximately 2 months. Refer to [section 4.1](#) for eligibility criteria to start cycle 1. For patients in MRD negative remission, it is required that patients have an ANC >200/ $\mu$ L or a sustained platelet count >20,000/ $\mu$ L before proceeding with cycle 2.

This form is to be completed and uploaded into RAVE at the end of every cycle.

Accession #

Patient COG ID number

Institution

Extensive details are in [Section 5.1](#) (treatment overview). This TDM extends to three pages.

DRUG	ROUTE	DOSAGE	DAYS	IMPORTANT NOTES																				
IT Cytarabine (AraC)	Intrathecal (IT)	Age-based dosing: 

Age	Dose	

< 1 year	20 mg	

≥ 1 to < 2 years	30 mg	

≥ 2 to < 3 years	50 mg	

≥ 3 years	70 mg	

	Age	Dose	< 1 year	20 mg	≥ 1 to < 2 years	30 mg	≥ 2 to < 3 years	50 mg	≥ 3 years	70 mg	Days 0 ^ , 7*, 14*, 21*, 28 ^	
^All patients. First time point given at the time of diagnostic lumbar puncture OR Day 0 for all patients. Note that Day 28 LP with IT chemotherapy of Cycle 1 counts as Day 0 LP with IT of Cycle 2. If the patient received IT cytarabine or triple IT therapy during their diagnostic workup within 14 days of starting protocol therapy, then they do not need additional Day 0 IT therapy.
 
*CNS 2/3 patients ONLY.
 
A minimum of 4 and a maximum of 6 weekly (count includes day 0 IT) intrathecal treatments may be given. The choice between IT Cytarabine OR IT Triples is up to the treating physician's discretion. See Section 5.1 for administration guidelines.
										
Age	Dose																							
< 1 year	20 mg																							
≥ 1 to < 2 years	30 mg																							
≥ 2 to < 3 years	50 mg																							
≥ 3 years	70 mg																							

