**Cycle 1-2**

	≥ 1	2000 mg/m  /dose once daily	Use eye drops as described in Section 5.2
--	-----	---	---

**NOTE;**The choice of intrathecal therapy, between cytarabine or cytarabine/methotrexate/hydrocortisone on Day 0 and on subsequent days for patients with CNS2 and CNS3 is at the discretion of the treating physician. CNS2 and CNS3 patients will receive additional IT cytarabine OR IT triples once weekly until the CNS is clear of blasts on 2 consecutive LPs, with a minimum of 4 IT cytarabine OR IT Triples doses administered (maximum of 6 intrathecal treatments).

Assigned Dose Level \_\_\_\_\_ Ht \_\_\_\_\_ cm Wt \_\_\_\_\_ kg BSA \_\_\_\_\_ m^2

Date Due	Date Given	Day	IT ARAC _____mg	IT Triples ARAC____mg MTX____mg HC____mg	LCV PO/IV _____mg	GMI-1271 IV _____mg	FLU IV _____mg	HD ARAC IV _____mg	Studies
Enter calculated dose above and actual dose administered below									
		PRE	_____mg^	_____mg^ _____mg^ _____mg^					a-k, m
		1			_____mg% _____mg%	_____mg			n
		2				_____mg _____mg	_____mg	_____mg	
		3				_____mg _____mg	_____mg	_____mg	
		4				_____mg _____mg	_____mg	_____mg	d
		5				_____mg _____mg	_____mg	_____mg	
		6				_____mg _____mg	_____mg	_____mg	n
		7	_____mg*	_____mg* _____mg* _____mg*		_____mg _____mg			a, d-g, m
		8			_____mg% _____mg%	_____mg _____mg			
		9							
		10							
		11							d
		12							
		13							
		14	_____mg*	_____mg* _____mg* _____mg*					a, d-g, m
		15			_____mg% _____mg%				
		16							
		17							d
		18							
		19							
		20							
		21	_____mg*	_____mg* _____mg* _____mg*					a, d-g, m
		22			_____mg% _____mg%				
		23							
		24							d
		25							
		26							
		27							
		28	_____mg^	_____mg^ _____mg^ _____mg^					a, b, d- h, l-m, o
		29			_____mg% _____mg%				

Please refer to [Section 8.1](#) for the specific timing of these observations.

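### Section 5.1.4 caps intrathecal treatments for CNS2/3 patients at six per cycle, while footnote 1 of Tables 1 and 2 reads as one cap of six across both cycles; the passages need reconciling.

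*Combined protocol and SAP*

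**What the plan says.** The limit on intrathecal treatment appears in several places, with different units.

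- **Section 5.1.4, CNS2/3 paragraph.** Weekly treatment continues until two successive lumbar punctures are clear, with at least four treatments and "with a maximum of 6 weekly intrathecal treatments per cycle". The same sentence adds that "these weekly treatments may carry over into Cycle 2 as needed to achieve CNS1 status". The paragraph ends by saying that a dose given during the diagnostic workup "counts within the minimum of 4 and maximum of 6 intrathecal treatments", this time without a period.
- **Tables 1 and 2, footnote 1.** "A minimum of 4 and a maximum of 6 intrathecal treatments may be given", followed by the rule that the "count includes day 0 IT and may carry over into Cycle 2 of chemotherapy".
- **Section 5.6, delivery map.** The intrathecal cytarabine row, the triples row and the note below them all give a minimum of four and a maximum of six. The note says only "maximum of 6 intrathecal treatments". None of the three names a period or mentions carry-over. The map is headed for Cycles 1-2 and is uploaded at the end of each cycle.
- **Schedule.** Section 5.1.4 lists Days 0, 7, 14, 21 and 28 for CNS2/3 patients, and Section 5.1 allows two cycles. On the overlap, the map says: "Note that Day 28 LP with IT chemotherapy of Cycle 1 counts as Day 0 LP with IT of Cycle 2". It marks Day 28 as applying to all patients.

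**The concern.** A count that carries over into Cycle 2 does not restart there. Footnote 1 therefore implies one allowance of six for both cycles, whereas Section 5.1.4 grants six in each. Section 5.1.4 is also not consistent within its own paragraph, since its last sentence repeats the maximum without a period. A site reading the footnote and a site reading Section 5.1.4 could treat the same patient differently in Cycle 2, and each could believe it was following the protocol.

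The treatment in question has recognised neurotoxicity. Section 6.3.1.2 warns of methotrexate leukoencephalopathy after intrathecal triples. The footnote to Table 14 says that leukoencephalopathy may be enhanced by systemic agents that include high-dose cytarabine, which every cycle contains. Section 6.3.1.1 takes patients with Grade 3 or 4 nervous system disorders off protocol therapy. Describing the toxicities of the combination is primary aim 1.1.3. In a study expected to need at most 22 patients (Section 11.1), each neurologic event carries weight, and intrathecal exposure that depends on the passage a site followed makes such events harder to interpret.

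**Working it through.** The six is a stated rule, not a derived figure, so there is no calculation in the plan to reproduce. The check is a count of treatment days under each reading.

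**Inputs**
- Intrathecal days per cycle for CNS2/3: 0, 7, 14, 21, 28, which is 5 (Section 5.1.4).
- Cycles: 2, each taken as 28 days (Section 5.1).
- Cycle 1 Day 28 is also Cycle 2 Day 0, so one day is shared (Section 5.6).
- Dose at age 3 or older: 12 mg methotrexate in triples (Table 4), or 70 mg intrathecal cytarabine (Table 3).

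**Step 1: treatment days available.** 5 + 5 − 1 = 9 distinct days: 0, 7, 14, 21, 28, 35, 42, 49 and 56, counted from Cycle 1 Day 0.

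**Step 2: what each reading permits**

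| Reading | Nominal ceiling | Reachable on the printed schedule |
|---|---|---|
| One running cap | 6 | 6 |
| Cap per cycle | 2 × 6 = 12 | 9 |

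A per-cycle cap of six does not bind here, because a 28-day cycle lists only five days. A running cap of six is used up on day 35, which is Cycle 2 Day 7.

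**Step 3: size of the difference.** 9 / 6 = 1.50, so the per-cycle reading allows up to 50% more. Seen from the other side, 1 − 6/9 = 33% fewer under the running cap.
- Methotrexate in triples: 6 × 12 = 72 mg; 9 × 12 = 108 mg.
- Intrathecal cytarabine: 6 × 70 = 420 mg; 9 × 70 = 630 mg.

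**Step 4: longer cycles (assumption).** Cycle 2 waits for count recovery, so cycles can exceed 28 days. Suppose weekly punctures continue and the last one before Cycle 2, where the cap permits it, serves as Cycle 2 Day 0. With one or both cycles lasting 35 to 42 days, the per-cycle reading then allows 10 to 12 treatments, 67% to 100% above six. For example, two 35-day cycles give 6 + 6 − 1 = 11.

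**Step 5: where the readings part.** Within Cycle 1 both readings stop at six, whatever the cycle's length. The first treatment that one permits and the other bars is the seventh, in Cycle 2. On the printed schedule a weekly seventh falls on Cycle 2 Day 14. If weekly dosing stops after Cycle 2 Day 7, the end-of-Cycle-2 dose is the seventh (0, 7, 14, 21, 28, 35, 56), and the text does not say whether it counts towards the cap.

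**The case against.** The strongest reply is that few patients could be affected. Weekly dosing stops after two successive clear punctures once four treatments are given. A patient who clears by Day 28 of Cycle 1 and then has only the end-of-Cycle-2 dose receives treatment on days 0, 7, 14, 21, 28 and 56. That is six under either reading. Reaching nine takes CNS2/3 disease, entry into Cycle 2 and CSF that stays uncleared well into that cycle. Isolated CNS disease is excluded (Section 4.2.1) and the study is small, so the group may be very small or empty. This stands: nine against six is a ceiling, not a typical difference.

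The reply can add that intrathecal methotrexate varies anyway, because the physician chooses between cytarabine and triples. That is true, but it is declared discretion. An unsettled maximum is not.

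Three stronger readings are tempting, and the documents do not support them.
- A reader might infer that the delivery map states a total cap. It gives six with no period, on a form completed each cycle, so it fits either reading. Even in footnote 1, a total is inferred from the carry-over wording; the word is not used.
- A reader might infer that a per-cycle cap of six is empty because only five days are listed. That holds only for exact 28-day cycles. The Day 28 dose may fall as late as Day 35, and a longer Cycle 1 can hold a sixth weekly dose.
- A reader might infer that dose finding is affected. The DLT window is Cycle 1 (Section 5.5) and pharmacokinetic samples are taken on Cycle 1 Days 1 and 6 (Section 8.3). The readings part only in Cycle 2.

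**Conclusion.** The conflict between Section 5.1.4 and footnote 1 of Tables 1 and 2 is real, and the delivery map does not resolve it. On exact 28-day cycles, with the Cycle 1 Day 28 dose counted once, the permitted maximum is six or nine treatments, up to 50% more under the per-cycle reading. The gap could be wider if cycles run longer. The milligram totals are the corresponding ceilings for patients aged 3 or older who receive the same intrathecal regimen throughout.

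The effect is confined to CNS2/3 patients who enter Cycle 2 and go beyond six treatments, chiefly those whose CSF has not cleared on two successive punctures. The protocol does not estimate their number. What is at stake is the safety of those patients and a consistent toxicity description under aim 1.1.3. The DLT/MTD rule and the pharmacokinetic analysis are not affected. This is a contradiction in wording that should be corrected, not a flaw in the statistical design. No view is taken here on which limit is right.

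**What to change.** Reconcile footnote 1 of Tables 1 and 2, the CNS2/3 paragraph of Section 5.1.4 (both sentences that give the maximum), and the two intrathecal rows and the note of the Section 5.6 delivery map. Each should state:

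- the same cap;
- the period it covers, either each cycle or both cycles together;
- how the Day 28 doses count: to which cycle the shared Cycle 1 Day 28 / Cycle 2 Day 0 dose belongs, and whether the end-of-Cycle-2 dose counts towards the cap.

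The choice of cap belongs to the study's clinical leadership. The cost is a short wording change in each of these places, with no added patients, samples or procedures.

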##### **5.1.4.1 Cytarabine: IT**

CNS 1 patients: Day 0 and 28\*

CNS 2/3 patients: Day: 0, 7, 14, 21, 28\*

Dose: age-based dosing

**Table 3 – Cytarabine IT Dosing by Age**

Age	Dose
< 1 year	20 mg
≥ 1 to < 2 years	30 mg
≥ 2 to < 3 years	50 mg
≥ 3 years	70 mg

##### **5.1.4.2 Intrathecal Triple Therapy (ITT): Methotrexate (MTX)/Hydrocortisone (HC)/Cytarabine (ARAC)**

CNS 1 patients: Day 0 and 28\* only

CNS 2/3 patients: Days 0, 7, 14, 21, 28\*

THIS PROTOCOL IS FOR RESEARCH PURPOSES ONLY, SEE PAGE 1 FOR USAGE POLICY

**Table 4 – ITT Dosing by Age**

Patient Age	Methotrexate	Hydrocortisone	Cytarabine
< 1 year	6 mg	12 mg	18 mg
≥ 1 to < 2 years	8 mg	16 mg	24 mg
≥ 2 to < 3 years	10 mg	20 mg	30 mg
≥ 3 years	12 mg	24 mg	36 mg

It is recommended, but not required, that weekly intrathecal therapy begin at least 24 hours after high dose cytarabine.

**Note:** CNS 2 and CNS 3 patients will receive additional IT cytarabine OR IT triples once weekly until the CNS is clear of blasts on 2 consecutive LPs, with a minimum of 4 IT cytarabine OR IT Triples doses administered.

\*Day 28 IT chemotherapy can be administered at the time of end of cycle bone marrow assessment between Day 28 and 35.

### 5.1.5 **Leucovorin : Oral (PO) or Intravenous (IV) FOR DOWN SYNDROME PATIENTS ONLY**

Days: 1, 8, 15, 22 and 29

Dose: 5 mg/m^2/dose x 2 doses given 24 and 30 hours after each **triple IT therapy** dose with methotrexate/hydrocortisone/cytarabine. Leucovorin administration is not necessary for patients receiving IT cytarabine.

Leucovorin rescue will be given after each ITT dose for patients with Down syndrome. The first dose to be given 24 hours after the lumbar puncture and the second dose to be given approximately 30 hours after the lumbar puncture.

Administer with or without food. Administer doses on schedule as determined by timing of methotrexate administration. If a dose is missed, administer dose immediately. Give the next scheduled dose according to the original dosing schedule. Do not deviate from the original schedule. Notify provider if a dose is delayed or missed.

## 5.2 **Criteria for Starting Subsequent Cycles**

A cycle may be repeated every 28 days up to 2 total cycles if the patient; 1) has at least stable disease; and, 2) all pre-cycle studies required per [Section 8.1 are obtained](#) and eligibility criteria as defined in [Section 4.0 are met](#); and, 3) is otherwise eligible to continue agent administration per the requirements in [Section 6.0](#)

For patients in MRD negative remission, it is required that patients have an ANC >200/μL or a sustained platelet count >20,000/μL before proceeding with cycle 2.

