#### 4.1.8 Organ Function Requirements

##### 4.1.8.1 Adequate Bone Marrow Function Defined As:

- a. For patients with leukemia:
  - Platelet count  $\geq 25,000/\mu\text{L}$  (may receive platelet transfusions).

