## 5.5.2 Hematological dose limiting toxicity

### 5.5.2.1 **In patients evaluable for hematological toxicity (see [Section 11.2.1](#)), hematological dose limiting toxicity is defined as:**

Failure to recover a peripheral ANC > 200/ $\mu$ L and non-transfusion dependent platelets > 20,000/ $\mu$ L by 43 days after the first treatment day with fludarabine and cytarabine, not due to malignant infiltration (including MRD by central flow cytometry analysis) or  $\geq$ Grade 3 infection or sepsis. Failure to recover peripheral counts due to disease involvement of the bone marrow will not be considered dose-limiting.

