### 6.1 Dose Modifications for Hematological Toxicity

6.1.1 Patients who experience a hematologic dose limiting toxicity defined as failure to recover a peripheral blood ANC > 200/ $\mu$ L and non-transfusion dependent platelet count > 20,000/ $\mu$ L by 43 days after the start of the cycle, not due to malignant infiltration or severe infection will be allowed to proceed to Cycle 2 at the next lower dose level at the discretion of the treating physician and study chair or vice-chair. If patient is starting at Dose Level -1, further de-escalation will not occur and the patient must be removed from protocol therapy.

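### Cycle 2 may start on recovery of one cell line, up to 16 days before the two-line hematological DLT is read, and no rule says how to classify such a patient

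*Combined protocol and SAP*

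**What the plan says.** - **Section 5.2** allows cycles to repeat at 28-day intervals. For patients in MRD negative remission it adds a count condition: ANC above 200/µL "or a sustained platelet count" above 20,000/µL. The therapy delivery map in Section 5.6 repeats it.
- **Section 5.2** also requires the Section 4.0 criteria. The only blood-count criterion there (4.1.8.1) is platelets of at least 25,000/µL, for which patients "may receive platelet transfusions". There is no ANC minimum.
- **Section 5.5.2.1** makes it a DLT not to recover ANC above 200/µL "and non-transfusion dependent platelets" above 20,000/µL "by 43 days after the first treatment day with fludarabine and cytarabine". Non-recovery caused by leukemia (including MRD) or by Grade 3 or higher infection or sepsis is excluded.
- **Section 6.1.1** uses the same pairing, ANC "and non-transfusion dependent platelet count", but counts the 43 days from the start of the cycle. It allows a patient with this DLT to receive Cycle 2 at the next lower dose level.
- **Table 1** says "Upon count recovery, patients may receive a second cycle of uproleselan (GMI-1271) in combination with fludarabine and cytarabine", without defining recovery.
- **Sections 5.5 and 5.1** set the DLT observation period as the first cycle and a cycle as 28 days.
- **Section 11.2.1**, which Section 5.5.2.1 cites for hematological evaluability, asks only for 85% of the prescribed dose and the appropriate toxicity monitoring. It has no hematological definition, although Section 11.1 lifts restrictions on heme evaluability for the PK cohort and so implies that some exist.
- **Section 11.3** accepts Dose Level 1 (DL1) with 0 or 1 DLT in six patients and treats the MTD as exceeded with 2 or more.

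**The concern.** The condition for starting Cycle 2 is met by either count; the DLT is avoided only by both. The first can apply about two weeks before the second is read. A patient with one line unrecovered can therefore receive further myelosuppressive chemotherapy while Cycle 1 DLT status is still open, and the plan does not say how that patient is scored. Because the DLT excludes non-recovery due to residual disease, patients in MRD negative remission are the main group in whom it can count, and they are the group to whom the either-count condition applies. At stake is the DLT count that selects the recommended dose, in a cohort of six where one patient can decide the outcome.

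**Working it through.** **1. The plan's own figure.** Section 11.1 expects at most 22 patients: six at each of two dose levels, six for PK, and 20% inevaluable. (6 + 6 + 6) × 1.2 = 21.6, rounded up to 22. It reproduces and is not disputed. It leaves 22 − 18 = 4 spare places, shared with PK failures, or 6 × 0.2 = 1.2 per cohort of six.

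**2. Timing.**
- Earliest Cycle 2 Day 1: 28 + 1 = Day 29. The delivery map agrees, since the Day 28 lumbar puncture counts as Day 0 of Cycle 2.
- First Cycle 2 fludarabine and cytarabine: Day 2 of that cycle, so Day 30.
- DLT reading under 5.5.2.1: Day 2 + 43 = Day 45.
- Reading under 6.1.1, if the cycle starts on Day 1: Day 1 + 43 = Day 44.
- Gap to the Day 45 reading: 45 − 29 = 16 days from Cycle 2 start; 45 − 30 = 15 days from its chemotherapy.

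**3. The count rules side by side, for a patient in MRD negative remission.**

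| Status before Cycle 2 | Written count conditions for Cycle 2 (5.2, 4.1.8.1) | If unchanged on Day 45 (5.5.2.1) |
|---|---|---|
| ANC 350/µL, platelets at least 25,000/µL only by transfusion | Met | DLT |
| ANC at most 200/µL, unsupported sustained platelets at least 25,000/µL | Met | DLT |
| Both recovered without transfusion, platelets at least 25,000/µL | Met | No DLT |

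Failing one line meets the whole DLT definition. Section 6.1.1 does not block the first two rows, because it applies only once non-recovery at 43 days is established.

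**4. Two possible scorings.** If Cycle 1 is taken as closed when Cycle 2 starts (5.5), the patient is DLT-free. If 5.5.2.1 is applied literally on Day 45, counts suppressed by Cycle 2 are read as a Cycle 1 DLT. The text supports either.

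**5. Effect on the decision.** Under 11.3, 1/6 makes DL1 the recommended dose. 2/6 exceeds the MTD, unless the exception in 11.2.2 for DLTs of different classes leads to expansion.

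**6. Illustration.** The documents give no DLT rates, so these are assumptions. With non-hematological risk a, hematological risk h and a share m of hematological DLTs uncounted, per-patient risk is p = 1 − (1 − a)(1 − h(1 − m)). P(DL1 passes) = (1 − p)^6 + 6p(1 − p)^5, ignoring the 11.2.2 exception.

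| a | h | All read (m = 0) | Half uncounted (m = 0.5) |
|---|---|---|---|
| 5% | 10% | 0.79 | 0.89 |
| 10% | 10% | 0.68 | 0.79 |
| 10% | 20% | 0.46 | 0.68 |
| 10% | 30% | 0.28 | 0.57 |

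In the other direction, with a = 10% and no true hematological DLT, falsely scoring 10% of patients lowers P(pass) from 0.89 to 0.68; falsely scoring 20% lowers it to 0.46.

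**The case against.** - **The deadline is explicit.** Section 5.5.2.1 fixes a date and exempts only leukemia and severe infection, not Cycle 2 therapy. A patient still unrecovered on Day 45 is a DLT on its literal terms. This stands against any claim that the DLT is simply lost. It does not make the reading interpretable after re-treatment.
- **The statements serve different purposes.** An eligibility floor, an added condition for MRD negative patients and a DLT definition can all apply together, and Table 1's wording might block the example. Partly right, but Table 1 leaves recovery undefined, so it settles nothing.
- **There is oversight.** Section 14.5.2 has the study chair enter evaluability and DLTs, with weekly review by the network's chair, vice chair and statistician. That is a useful control, but not a pre-specified rule.
- **The event may be rare.** Section 2.3.1 reports 41% CR/CRi in relapsed or refractory adults, of whom 69% were MRD negative: 0.41 × 0.69 = 28%. The backbone differs, so this is an assumption. If 20% to 50% of these had single-line failure, the rate would be 6% to 14% of patients, and two or more in six would have probability of about 4% to 20%, before requiring early re-treatment and misclassification. This makes the 10% hematological rows more relevant than the 20% and 30% rows. A single such patient is enough, however, where another DLT has occurred.
- **Excluding slow recoverers can itself bias the count low.** This stands, and the fix has to guard against it.

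**Conclusion.** The mismatch is real and appears in both places that state the Cycle 2 count condition. Following the plan as written can make a component of the primary endpoint unreadable over a gap of 15 to 16 days, and one patient can reverse the DL1 decision. Day 29 is the earliest case: the marrow that establishes MRD status may be taken on any of Days 28 to 35 and is read centrally, so the gap will often be shorter. The probabilities above rest on assumed rates and show sensitivity only.

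A reader might infer more than this:
- *That Cycle 2 erases a Cycle 1 DLT and biases the count low.* Before Day 45 the status is unread, not established; a declared DLT falls under Section 6.1.1 and remains. A false DLT is equally possible, so the direction is undetermined.
- *That the plan releases MRD negative patients early.* The Section 5.2 sentence adds a condition for them; other patients have no ANC condition there.
- *That only MRD negative patients can have this DLT.* The exclusion turns on the cause of non-recovery, so they are the principal group, not the only one.
- *That the count would fall from 2/6 to 0/6.* That needs two such patients, both re-treated early and both scored DLT-free. A change of one is the defensible size.

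**What to change.** 1. Reconcile Table 1 and Sections 5.2, 5.5.2.1, 5.6 and 6.1.1 on the count-recovery condition and on the day from which the 43 days run. The clinical team decides which rule applies.
2. Add to Section 11.2.1 the hematological evaluability definition that Section 5.5.2.1 cites. State that a patient who starts Cycle 2 or other cytotoxic therapy before the 43-day reading with either line unrecovered is not counted as free of hematological DLT. Classify such patients by a pre-specified rule and replace them if inevaluable. Any non-hematological DLT still counts.
3. Because this exclusion may be informative, report how many patients it affects and show the dose decision also with each of them counted as a DLT.

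The cost is wording, plus possibly one or two replaced patients, to be met from the existing 20% allowance. That allowance is 1.2 patients per cohort of six and is shared with PK failures. The planned sample size need not change.
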